7.0 Study Completion

7.1 Completed Subjects

Subjects who complete the 6-month crossover study will be provided with the option to upgrade to a compatible sound processor. This option must be redeemed within 5 years from completion of the study. At the end of their participation, all subjects will return to the ACE strategy and will be fitted with their personal sound processor. Because subjects will not use their personal sound processors for the first 6 months after surgery, the device warranty for the personal sound processor will be extended by 6 months, and the trial period will be 90 days from the fitting of the personal sound processor. During the 90-day trial period, subjects will have the option to exchange their personal sound processor for another commercially available device. Subjects will also receive an expanded 5-year warranty on all parts and pieces included in their personal sound processor kit. Subjects will continue to receive standard clinical follow-up care after the completion of the study.

7.2 Discontinued Subjects

Subjects who withdraw or are discontinued prior to the completion of the 6-month visit will receive compensation of \$12.50/ hour for the cumulative period of time spent on study procedures. This payment will be in lieu of the option for a processor upgrade. This is outlined clearly in the patient informed consent form. All subjects will return to the ACE strategy and will be fitted with their personal sound processor.

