1.2 Sample Size

Based on the variability observed in the FAST take-home trial in experienced ACE recipients, it was determined using G*Power (Faul et al. 2007) that a minimum of 11 subjects would provide at least 90% power for hypothesis testing of the two co-primary endpoints at the 0.025 alpha level. More subjects will provide additional power or a similar degree of power for more conservative assumptions. Because the non-inferiority sample size calculation assumes a true difference of 0 between ACE and FAST, we propose a sample size of 20 subjects to allow for:

1. the possibility that variability will be greater than expected,
2. the possibility of a clinically insignificant difference between the two strategies,
3. the possibility of subject attrition.

The planned sample size of 20 subjects will provide adequate power for the primary efficacy endpoints. The following general assumptions have been made:

- Non-inferiority tests with M_2 margins of 10 rationalized arcsine units (rau, Studebaker 1985) for CNC word recognition and -2 dB for average BKB sentence recognition across two types of noise (babble and speech-shaped noise)
- One-sided 0.025 alpha levels
- Assumed distribution for population (standard deviation) based on the FAST take-home trial in experienced ACE recipients
- Desire for 90% power

The power analyses for the primary test metrics are provided below.

Sample size calculation for CNC word recognition:

Scenario (Non-inferiority)	Minimum Evaluable Sample Size Required
One-sided 0.025 alpha, 90% power, SD = 7.20 rau, $M_2 = 10$ rau, true difference = 0	8

Sample size calculation for BKB sentence reception (using previous data from testing in babble only):

Scenario (Non-inferiority)	Minimum Evaluable Sample Size Required
One-sided 0.025 alpha, 90% power, SD = 1.84, $M_2 = -2$ dB, true difference = 0	11

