1.4.1 Primary Efficacy Objectives

The two co-primary efficacy endpoints will be based on analyses of CNC word recognition and BKB sentence reception in babble and speech-shaped noise after 3 months of experience with each strategy (collected at 3-months and 6-months post initial activation). The objective of the two co-primary efficacy endpoints is to test for non-inferiority of FAST compared to ACE. Study success will be defined by rejection of the null hypotheses for both of the two co-primary endpoints.

1.4.1.1 *First Co-Primary Efficacy Endpoint: CNC Word Recognition*

The objective of the first co-primary efficacy analysis is to demonstrate non-inferiority of FAST compared to ACE for word recognition in quiet as evaluated with the CNC test. Success for the first co-primary endpoint will be based on rejection of the null hypothesis of inferiority, with a non-inferiority margin of 10 rau based on clinical judgment and variability observed in previous studies ($M_2 = 10$). The treatment effect will be estimated using a LMM adjusted for period and sequence and a random effect for subject. If the upper 97.5% confidence bound is less than 10 rau, statistical significance will be met at the 0.025 alpha level. The first co-primary endpoint is represented by the following hypotheses:

$$H_0: CNC_{diff} \geq 10 \text{ rau},$$

$$H_a: CNC_{diff} < 10 \text{ rau},$$

where:

CNC_{diff} = ACE – FAST treatment difference, controlling for period and sequence effects, for CNC word recognition in rationalized arcsine units (rau).

1.4.1.2 *Second Co-Primary Efficacy Endpoint: BKB Sentence Reception in Noise*

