1.9 Missing Data

All efforts will be put forth to ensure near complete follow-up, with particular focus on the assessment of the primary outcomes and occurrence of adverse events. A reminder of subject follow-up due dates will be provided to participating centers to facilitate scheduling of the follow-up visits.

Sensitivity analysis will be conducted to address the potential impact of missing endpoint data using a multiple imputation analysis with 10 imputed datasets. A separate imputation model will be performed for each primary outcome variable (CNC score and average SRT). The predictor variables in the model will include, but are not limited to, the three target variables in the primary endpoint analysis (treatment, period, and sequence), and five auxiliary variables to improve the estimation of missing datapoints (Reading Span score, age, duration of hearing loss, pre-operative sentence score, and duration of hearing aid use). The imputed datasets will then be combined for inference using standard methods such as those available in SAS PROC MIANALYZE or other valid statistical software.

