5.5 Postoperative Procedures

5.5.1 Visit 2

Visit 2 will be conducted at the Clinical Sites. Procedures will include initial activation and mapping of the first strategy (Group 1 will receive FAST, and Group 2 will receive ACE). Subjects will be oriented to use of the CP810 processor.

5.5.2 Visit 3

Visit 3 will be conducted at the Clinical Sites. Procedures will include fine-tuning of the initial strategy.

5.5.3 Visit 4

Visit 4 will be conducted at the Clinical Sites. The first battery life questionnaire will be handed out to the subject, and instructions for completing and returning

CONFIDENTIAL

the questionnaire will be provided. Mapping will be conducted for fine-tuning of the initial strategy.

5.5.4 Visit 5

Visit 5 will include endpoint speech perception tests, the Reading Span Test, clinical audiological testing, and programming of the crossover strategy. Depending on the Clinical Site, endpoint speech testing (CNC words and BKB sentences) and the Reading Span Test will be conducted either at the Clinical Site or at the Denver Research & Technology Labs (Cochlear Americas). All programming will be conducted at the Clinical Sites. Since endpoint speech testing will be administered by a clinician blinded to the current treatment, endpoint speech testing and programming will be performed by different clinicians. The crossover strategy will be programmed (Group 1 will receive ACE, and Group 2 will receive FAST), and the acute sound quality ratings will be conducted.

5.5.5 Visit 6

Visit 6 will be conducted at the Clinical Sites. Procedures will include fine-tuning of the crossover strategy.

5.5.6 Visit 7

Visit 7 will be conducted at the Clinical Sites. The SSQ12-C will be completed, and the second battery life questionnaire will be handed out to the subject. Mapping will be conducted for fine-tuning of the crossover strategy.

5.5.7 Visit 8

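### A subject who stops FAST early leaves no FAST score, and the one planned missing-data check would not show the resulting bias towards non-inferiority if subjects stop because FAST works poorly

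*Combined protocol and SAP*

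**What the plan says.** **Leaving early.** Protocol 7.2 opens: "Subjects who withdraw or are discontinued prior to the completion of the 6-month visit will receive compensation of" an hourly sum, in place of the processor upgrade offered to completers. It then says: "All subjects will return to the ACE strategy and will be fitted with their personal sound processor". It asks for no endpoint test before the return to ACE. Protocol 7.1 covers completers: "Subjects who complete the 6-month crossover study will be provided with the option to upgrade to a compatible sound processor".

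**When endpoints are measured.** Protocol 5.5 and Table 1 schedule the CNC and BKB endpoint tests at two visits only. One is month 3: "Visit 5 will include endpoint speech perception tests, the Reading Span Test, clinical audiological testing, and programming of the crossover strategy". The other is Visit 8 at month 6.

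**Primary analysis.** For each co-primary endpoint, SAP 1.4.1 says: "The treatment effect will be estimated using a LMM adjusted for period and sequence and a random effect for subject". The SAP text defines no analysis set.

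**Missing data.** SAP 1.9 says: "Sensitivity analysis will be conducted to address the potential impact of missing endpoint data using a multiple imputation analysis with 10 imputed datasets". The named predictors are the three model terms (treatment, period, sequence) plus "five auxiliary variables to improve the estimation of missing datapoints". Those five are age, the Reading Span result, how long the subject has had a hearing loss, how long hearing aids were worn, and the sentence score before surgery. The list is left open. No scenario other than missing at random is described.

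**Expectation of loss.** SAP 1.2 gives "the possibility of subject attrition" as one reason for enrolling 20, without a rate. Protocol 9.2 names difficulty in converting to the second strategy as a risk, reports that some experienced ACE users had trouble adapting to FAST over 18 weeks, and points to the option to withdraw.

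**The concern.** Study success is a claim that FAST is not worse than ACE by more than the margin. The subjects most likely to give up FAST are those for whom it works badly, and under 7.2 they give it up without being tested on it. Group 2 is the more visible case, because it moves from ACE to FAST at month 3, the direction in which 9.2 reports difficulty. Such a subject contributes an ACE score only. A Group 1 subject who stops in the first three months contributes nothing.

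The mixed model treats the absent FAST scores as predictable from the observed data. The imputation does the same: no named predictor records how FAST worked for that subject, so it supplies a FAST score like those of similar subjects who stayed. The two analyses would therefore tend to agree, and their agreement would look like robustness. At stake is a non-inferiority conclusion that a few unobserved subjects could have reversed.

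**Working it through.** **Inputs.** From SAP 1.2 and Protocol 8.2: one-sided alpha 0.025; CNC margin 10 rau, SD 7.20 rau; SRT margin 2 dB in size, SD 1.84 dB (stated in 8.2 to be the SD of difference scores); 20 subjects. From Protocol 5.1: half in each sequence, so 10 per group. Assumptions, because the documents give no figure: the number of stoppers k, and how closely stopping follows a poor FAST result.

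**Reproducing the plan's figures.** A paired non-inferiority t-test with true difference 0 has power 0.918 at n = 8 for CNC (0.862 at n = 7) and 0.900 at n = 11 for SRT (0.863 at n = 10). The stated 8 and 11 are right. With 16 evaluable subjects SRT power is still 0.981, so power is not the problem.

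**Size of the shift.** Let d be each subject's difference, signed so that positive means FAST is worse. Set its true mean at the margin and its SD at the documented value. Remove the k largest d from Group 2. Estimate the effect as the average of the two group means.

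The four largest of 10 standard normal values have expected values of about 1.54, 1.00, 0.66 and 0.38. The remaining Group 2 mean falls by (sum of the k largest)/(10 − k) SDs, and the treatment estimate falls by half of that.

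| k | shift in SDs | CNC shift | CNC estimate (true 10) | SRT shift | SRT estimate (true 2) |
|---|---|---|---|---|---|
| 1 | 1.54/9/2 = 0.086 | 0.62 rau | 9.38 | 0.16 dB | 1.84 |
| 2 | 2.54/8/2 = 0.159 | 1.14 rau | 8.86 | 0.29 dB | 1.71 |
| 4 | 3.58/6/2 = 0.298 | 2.15 rau | 7.85 | 0.55 dB | 1.45 |

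**Chance of falsely passing an endpoint.** Simulation of the same set-up on complete pairs, with pooled SD and n − 2 degrees of freedom (nominal 2.5%):

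| Link between stopping and a poor FAST result | k = 1 | k = 2 | k = 4 |
|---|---|---|---|
| none (correlation 0) | 2.5% | 2.5% | 2.5% |
| moderate (correlation 0.5) | 4% | 5% | 8% |
| complete (the worst results are missing) | 6% | 11% | 22% |

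The rates are the same for CNC and SRT to the nearest percent. The selection acts in SD units and each test is taken at its own margin, so the SD cancels.

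**Check with an all-available-data mixed model.** This keeps the stoppers' ACE scores. For SRT, with the worst Group 2 results missing, variances treated as known and an assumed between-subject SD of 2 to 4 dB, the rate is 6% to 7% for k = 2 and 11% to 16% for k = 4. The inflation is smaller but does not disappear.

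**The case against.** **The SAP does have a missing-data rule.** True, and its predictor list is open. Reading Span is a named predictor and was included with adaptation in mind. It is measured only at Visit 5, however, so it is unavailable for a Group 1 subject who stops earlier, and it is not a measure of how FAST worked. The rule stays within missing at random.

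**Early stopping may be rare.** The upgrade goes only to completers, which encourages staying. Candidates unwilling or unable to comply are excluded. The difficulty in 9.2 was seen in experienced ACE users, and newly implanted subjects were chosen to avoid that. All of this stands. It lowers the likely number of stoppers, and with none there is no effect.

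**Three stronger readings are tempting but unsupported.**
- A reader might infer that early stopping necessarily biases the result. It does not: the first row of the simulation table shows no inflation when stopping is unrelated to FAST performance.
- A reader might infer that a subject put back on ACE could attend Visit 8 and have that ACE score counted as FAST. No section provides for this. Protocol 3.2 requires different firmware for each strategy, 5.5.7 lists endpoint testing before final programming, and SAP 1.4.1 defines the endpoint after 3 months on each strategy. The general deviation clause in 16.0 does not forbid it, so a one-line rule is worthwhile, but it is not a finding about the plan.
- A reader might give each stopper a large fixed FAST deficit on top of the full documented SD and obtain far higher error rates. With 4 of 20 stoppers at 20 rau, that deficit alone contributes variance 0.2 × 0.8 × 20² = 64, more than the whole documented 7.20² = 51.8. Such rates need more variability than the plan assumes.

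**The remedy leaves the primary model's error rate unchanged.** Correct. A tipping-point analysis shows how far the conclusion depends on the missing scores; it does not recover them.

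**Conclusion.** The concern holds as a conditional one. As written, the plan sends early stoppers back to ACE untested, and it analyses and checks the gaps under the same missing-at-random assumption. If stopping follows poor FAST performance, which 9.2 makes plausible but does not quantify, the estimate moves towards non-inferiority and the planned check would not show it.

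With the worst Group 2 FAST results missing and the true difference at the margin, the false-pass rate for one endpoint is about 6%, 11% and 22% for 1, 2 and 4 stoppers, against 2.5%. It is about 4%, 5% and 8% if the link is moderate, and unchanged if there is none. Four stoppers would be 40% of Group 2, a case with no basis in the documents beyond illustration. Since both endpoints must pass, each figure is an upper limit for false study success in its scenario, approached only when the other endpoint is almost sure to pass. Confidence is medium, because k and the strength of the link are assumptions. The change should be made, since it is cheap and has to be specified before the data are seen.

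**What to change.** In SAP 1.9:

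1. Add a tipping-point (delta-adjusted) analysis. Shift the imputed FAST scores of early stoppers against FAST, for example by 0 to 30 rau downwards for CNC and 0 to 6 dB upwards for SRT, and report the shift at which non-inferiority is lost. A shift D applied to k Group 2 stoppers moves the estimate by kD/20. Undoing the k = 2 bias above therefore takes 1.14 × 20/2 = 11.4 rau or 0.29 × 20/2 = 2.9 dB, well inside these ranges.
2. Add the crossover sound-quality rating to the imputation model, and SSQ12-C where available. Both are already collected. Neither exists for a Group 1 subject who stops before month 3, so for that subject the tipping-point analysis is the main safeguard.
3. Record the strategy in use at each endpoint test, and state that a score obtained on ACE is not analysed as FAST.
4. Report early stops by strategy, group and reason.

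Optional, in Protocol 7.2: where the subject is willing, run the endpoint tests before early reprogramming, for sensitivity analysis only. Such scores reflect less than 3 months on FAST, need a blinded tester at short notice, and the timing could hint at the strategy.

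The definition of completion in 7.1 can stay as it is; changing it would weaken the incentive to remain on the assigned strategy. Sample size, margins and endpoints are untouched. The cost is a little more analysis work, and a conclusion that may look less robust if several subjects stop.

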7.3 Premature Study Termination

The Sponsor may terminate the study early in the case of major non-adherence to the protocol, or if it is anticipated that recruitment will not be met for the required number of subjects to complete the study objectives. In the event of premature study termination, the subjects who are already enrolled will be sponsored through study completion.

8.0 Data Analysis

8.1 Statistical Analysis

Endpoint speech perception data will be analyzed using linear mixed models (LMM) in order to test for treatment effects while controlling for period and sequence effects. Non-inferiority will be tested with the confidence intervals of the treatment effects from the statistical models. If the one-sided limit of the 97.5% confidence bound does not exceed the non-inferiority margin, statistical

CONFIDENTIAL

significance will be met at the 0.025 alpha level. The non-inferiority margin for word recognition is 10 rationalized arcsine units (rau). The non-inferiority margin for the sentence in noise tests with an adaptive SNR is –2dB. The non-inferiority margins are based on clinical judgment and variability observed in previous studies testing FAST and ACE.

8.2 Sample Size

Sample size calculations were conducted using G*Power 3.1 under the following general assumptions:

- Non-inferiority tests with margins of 10 rau for CNC word recognition and –2 dB for sentence reception in noise
- One-sided 0.025 alpha level
- Assumed distribution for population (standard deviation) based on a previous FAST take-home trial in experienced ACE recipients
- Desire for 90% power

To reject the null hypothesis of inferior CNC word recognition for FAST compared to ACE (using a standard deviation of 7.20 rau), a sample size of 8 subjects is required.

To reject the null hypothesis of inferior sentence reception in noise for FAST compared to ACE (using a standard deviation of difference scores of 1.84 dB), a sample size of 11 subjects is required.

An increased sample size of 20 subjects will be enrolled, which will allow for the possibility of subject attrition as well as providing a similar degree of power under more conservative assumptions.

8.3 Additional Statistical Analyses

Statistical analysis for this study is addressed in detail in the document entitled “Statistical Analysis Plan for Investigation of the FAST Sound Coding Strategy in Newly Implanted Adult Cochlear Implant Recipients.”

9.0 Risk Benefit Statement

9.1 Benefits

It is possible but not guaranteed that advances to cochlear implant technology will improve performance or usability of devices for future recipients. This investigation will help to inform the future development of the FAST strategy and

CONFIDENTIAL

the planning of future studies of FAST in the newly implanted population. There are no direct benefits anticipated for subjects participating in this study.

9.2 Risks

With any cochlear implant program, there is a very small risk of unintentional over-stimulation. Subjects may experience sounds in mapping that are uncomfortably loud.

There is a risk that recipients may experience difficulty converting from the initial strategy to the crossover strategy. It is known from previous studies with experienced cochlear implant recipients that the experimental FAST strategy can sound very different in quality to the default ACE strategy. Some experienced ACE recipients have struggled to adapt to the FAST strategy over an 18-week period. The conversion risk is clearly identified in the patient informed consent form. The consent form also clearly indicates the option to withdraw from the study at any time.

Subjects will not be able to use their personal sound processor until the completion of the study. Instead, they will be loaned the CP810 sound processor for the duration of their participation. The CP810 processor has been shown to have similar general performance outcomes to the Nucleus 6, Kanso, and Nucleus 7 sound processors. However, during study participation, subjects will not have access to some advanced features (adaptive directionality, SmartSound iQ, wireless accessories, and iPhone compatibility). These differences are clearly explained in the patient informed consent form. At the end of the trial, subjects will be fit with their personal sound processor and will have access to the full range of features that are commercially available at that time.

10.0 Good Clinical Practices Statement

The study obligations for the Investigator(s) are outlined in guidelines for Good Clinical Practice (GCP), ISO14155:2011 (Clinical Investigation of Medical Devices for Human Subjects – Good Clinical Practice), and the Declaration of Helsinki.

11.0 Access to Study Documents and Study Monitoring

Investigator(s) will provide access to study documentation including source data for the purposes of monitoring, audits, IRB review, and regulatory inspections.

CONFIDENTIAL

IDE #G150140 V2.4 September 28, 2017

Page 21 of 24

CAM-CL-111_F

Rev. 1

12.0 Quality Control and Assurance

Study sites may be subject to Quality audits at any point during the study. Regulatory agencies may conduct inspections during the course of the clinical investigation and after study completion.

13.0 Institutional Review Board

The final version of the IDE protocol will be submitted to the Western Institutional Review Board (WIRB®), and written approval obtained, before patients are recruited and subjects are enrolled. Each site will obtain approval from its designated IRB prior to commencing any study-related activities. A copy of the IRB approval will be kept in the Investigator file(s). Any additional requirements imposed by the IRB and/or regulatory authority shall be followed. The Investigator(s) will submit the appropriate documentation if any necessary extension or renewal of the IRB approval must be obtained.

